# **3.3 Exploratory endpoint**

Determination of various potential predictors of PTC by evaluating demographic, clinical and biological parameters. (see section 8.3).

# 4. SUBJECTS, POPULATION & SELECTION

### 4.1 Settings, selection & recruitment:

The participants will be recruited during a 21 months period from the patients regularly followed at the HIV reference centers of each partner (ITM, UZG, UZB, UMC Saint-Pierre). Potential participants will be informed on the study either by the local study team or during the consultation by the treating physician according to local customs.

# 4.2 Inclusion and exclusion criteria

In order to be eligible, study participants **must meet all the following inclusion criteria**:

- Able and willing to provide written informed consent.
- Men and women age  $\geq 18$  and < 65 years.
- Confirmed HIV-1 infection at any time prior to study entry.
- Infected with HIV-1 subtype A, B, C, D, CRF01\_AE and CRF02\_AG
- Participant should take ART for at least 2 years before baseline with no changes in the ART regimen for at least 90 days prior to study entry. ART regimen is defined as a mono- or bitherapy or a combination of three or more active antiretroviral drugs
- CD4 T-cell count is  $\geq 500/\mu l$  for a period of at least 3 months prior study entry

- Nadir CD4+ T-cell count is ≥300/µl. A lower nadir CD4+ T-cell count will be allowed if measured at time of acute infection as far as the relative CD4+ count remains above 20%. An acute infection is defined as an association of a clinical picture of retroviral syndrome together with a seroconversion in HIV serology or an incomplete confirmation test.
- Plasma viral load < 50 copies/ml for at least 2 years before baseline. (Occasional "blips" will be permitted if it happened more than six months before study entry. An occasional blip is defined as an intermittent viremic episode with a viral load above detection level but below 200 copies/ml and a return to an undetectable level in a next control).
- Willingness to complete scheduled assessments and participant visits.
- All female participants of childbearing potential should have a negative pregnancy test. These women and their partner should use double barrier contraception during the study.

Females of reproductive potential will need a negative serum or urine pregnancy test at screening. They are defined as those who have not reached menopause or been post-menopausal for at least 24 consecutive months, who have had menses within the preceding 24 months, or women who have not undergone surgical sterilization, specifically hysterectomy, or bilateral oophorectomy or tubal ligation).

NOTE: Acceptable documentation of hysterectomy and bilateral oophorectomy, bilateral salpingectomy, tubal micro-inserts, partner who has undergone vasectomy, and menopause is participant-reported history.

All participants must agree not to participate in a conception process (e.g., active attempt to become pregnant, sperm donation, or in vitro fertilization).

• Adequate peripheral vein access to perform leukapheresis

Participants meeting any of the following exclusion criteria will not be enrolled in the study:

- Previous or current history of AIDS defining event as defined in category C of the CDC clinical classification[39] .
- Any acute infection or serious medical illness within 60 days prior to study entry. Participants will be excluded from this study for a serious illness (requiring systemic treatment and/or admission) until the subject either completes therapy or is clinically stable on therapy, in the opinion of the Investigator, for at least 14 days prior to study entry
- History of resistance to antiretroviral drugs, documented by genotyping.
- Active hepatitis B or C virus infection: as defined with a positive serology for either disease with signs of active viral replication?
- Significant risk of HIV transmission during treatment interruption in the opinion of the investigator. This includes evidence for unsafe sexual contacts.
- Current or past history of cardiomyopathy or significant ischemic or cerebrovascular disease.
- History of HIV-related thrombocytopenia.
- Active renal disease (defined as a glomerular filtration rate (calculated by MDRD equation) below 50 ml/min or the presence of HIV associated nephropathy in the past medical history.

- Current or known history of cancer (with the exception of in situ cervix carcinoma or squamous cell carcinoma of the skin) within five years prior to screening.
- Pregnancy and breastfeeding.
- Any condition, including psychiatric and psychological disorders that might interfere with adherence to study requirements or safety of the participant.
- Prior use of any HIV vaccine and/or non-established experimental therapy
- Any of the following laboratory test results at screening:
  - 1. Confirmed hemoglobin <11g/dl for women and <12 g//dl for men
  - 2. Confirmed platelet count  $< 90,000/\mu$ l
  - 3. Confirmed neutrophil count <1200/µl
  - 4. Confirmed AST and/or ALT > 5 x upper limit on normal range (ULN). One retest within 14 days is allowed.
- Receipt of any immune modulator or suppressor within 30 days prior study entry, including, but not limited to drugs such as corticosteroids (with the exception of corticosteroids used for topical use), granulocyte-macrophage colony-stimulating factor, interleukin (IL)-2, IL-7 and IL-15.
- Active drug or alcohol use or dependence that, in the opinion of the site investigator, would interfere with adherence to study requirements.
- Participation in other interventional studies involving an investigational drug.

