HIV research is challenged by the concept of inducing "functional cure" or HIV remission, i.e. interventions aiming at keeping the viral load at low or undetectable levels after interrupting cART in infected patients. It has been suggested that so called "elite controllers" (EC) may provide important clues in this quest [9]. By definition EC are able to maintain their pVL "spontaneously" below the lower limit of detection i.e. without ever being treated with cART (or other regimens) [10,11]. Importantly, reports have recently emerged describing patients maintaining pVL below the lower limit of detection after interruption of long-time cART. These patients have been referred to as "secondary controllers" [12] or "post treatment controllers" (PTC) [13]. Conceptually, this status may provide additional and potentially more relevant information to develop strategies aiming at HIV cure.

The undetectable pVL in EC has been shown to be associated with low proviral DNA in peripheral blood CD4+ T cells and other reservoirs (e.g. the gut-associated lymphoid tissue) and with low or absent intracellular viral RNA. Some genetic host factors (e.g. the HLA types B27 and B57) as well as viral genetic characteristics (e.g. defects in Nef, Vif or other genes) are known to be associated with the EC phenotype. In the majority of the EC, HIV-specific CD8+ T- cell response has been shown to be qualitatively superior to the response seen in progressors. With this regard, HIV-specific CD8+ T cells targeting conserved viral proteins (e.g. Gag), exhibiting a polyfunctional cytokine production pattern, recognizing a broad array of epitopes and/or characterized by a high avidity have been shown to correlate with a better clinical outcome. However, the most consistent finding in EC is the presence of CD8+ T cells with a high "virus-suppressive/cytolytic" activity. Consequently, even in the absence of viral genetic defects, the replication capacity of HIV strains isolated from EC has been shown to be lower than what is seen in progressors [14].

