Four patients followed at ITG, who initiated cART during the chronic viremic phase, durably maintained control over viral replication after interruption (for varying reasons) of long-term cART [12]. No particularities were highlighted when evaluating the HIV-specific T-cell responses. Although no HLA-association or CCR5A32 polymorphism was observed, all four PTC had a low viral reservoir when compared to non-controllers, as assessed by PBMCassociated total HIV DNA. In addition, no intracellular viral unspliced mRNA species could be measured, suggesting a status of "silent" provirus. Finally, VOA from autologous CD4+ T cells repeatedly failed in one patient and showed delayed kinetics and low fitness in two others. With respect to viral characteristics the latter secondary controllers were rather similar to EC (low proviral load, low intracellular HIV mRNA and difficult-to-culture viruses). They were also clearly different compared to viremic progressors or aviremic subjects under continuous cART (from whom HIV could be easily cultured in vitro and who had higher HIV DNA and intracellular HIV mRNA). Five years following TI and although lacking viral rebound, two PTC were restarted on cART because of low CD4+ T cell counts [12]. Similarly, the SALTO study showed that 7 out of 95 chronically-infected HIV patients were able to control viral replication below the 400 copies/mL 12 months after long-term cART interruption[28]. Again, in these patients, the only associated predictive factor for viral control in this early treated chronic population was a low level of blood cell associated HIV DNA.

Thus, recent data provide sufficient evidence that a small proportion of HIV-1 infected subjects is able to spontaneously maintain viral suppression after interruption of long-term cART. This observation challenges the common wisdom that cART needs to be taken lifelong to prevent viral rebound and disease progression [29]. Although most PTC described in the medical literature so far initiated cART in the acute phase of the infection, there is emerging evidence that some patients, who started cART in the chronic progressive phase of the infection, are also able to control viremia following TI. Based on the observations in the VISCONTI, PRIMO and SALTO cohorts it is estimated that between 5 to 15 % of patients initiated on cART at the acute phase of the disease might spontaneously control viral replication following TI [13].

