# 5.1.3 SECOND SCREENING AND ENROLMENT IN THE SECOND PART OF THE STUDY (TREATMENT INTERRUPTION STUDY)

Study participants meeting the criteria for TI will be contacted preferably within one to three months after the first screening visit. Treatment interruption will be proposed to these participants with the lowest viral reservoir and consenting with the second phase of the study (second written informed consent). The criteria allowing treatment interruption are:

- Undetectable level of total HIV DNA (i.e. < 66 copies/  $10^6$  PBMC).

- Undetectable level of unspliced cell-associated RNA (i.e. <10 copies/10^6 PBMC).

Those criteria are based on previous research from the HIV Translational Research Group in UZ Gent [40].

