This is a single arm multi-centric non-randomized (prospective) clinical trial. The study will be divided in two parts. The first one will aim at quantifying the HIV reservoir in a large group of patients under ART with strictly predefined inclusion and exclusion criteria. The second step encompasses an analytical treatment interruption among participants with the lowest viral reservoir.

2.2. Study objectives and Hypotheses

Primary Objective

The primary objective is to determine the proportion of post treatment controllers (PTC) (i.e. patients under cART with low baseline peripheral blood proviral DNA that will show sustained viral suppression at 48 weeks post treatment interruption (TI).

Secondary Objectives

a. To confirm the safety of a TI strategy in selected HIV patients

b. To assess the viral reservoir magnitude prior, during and after TI

c. To assess the viral and host dynamics in those participants with viral rebound post TI.

Exploratory Objective

- a. The identification of predictors (clinical and/or laboratory) of PTC phenotype.
- b. The identification of predictors for viral rebound over time.

2.3. Variables of interest

Primary: The proportion of participants with plasma viral load (pVL) below the lower limit of detection (< 50 HIV RNA copies/ml plasma) 48 weeks following interruption of ART.

Secondary:

- The numbers and percentages of AE's and SAE's during the whole study period.
- Viral reservoir (total HIV-1 DNA) and viral transcription (total HIV-1 cellassociated RNA) measurements at every visit between baseline (just before TI) until viral rebound and 12 weeks after viral rebound.
- Repeated pVL measurements.

Exploratory: Potential clinical and/or laboratory variables, such as demographic and epidemiological data, medical history (past and current), vital parameters, ultrasensitive HIV viral load, CD4 T cell count and laboratory test data (e.g. hemoglobin, ANC, platelets, creatinine, AST & ALT), viral reservoir (quantitative viral outgrowth measurement) and viral release measurements (spontaneous and stimulated) at baseline.

3. Description of study population

3.1. Analysis populations

The statistical analyses will be performed on all participants enrolled in the study and who met all inclusion and exclusion criteria. Complete case analysis will be performed for all statistical analyses.

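### Viraemia before ART is neither an entry criterion nor an analysis variable, so a participant who already controlled HIV before ART would be counted as a post-treatment controller

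*Protocol*

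**What the plan says.** **Eligibility (Protocol 4.2).** The infection criterion is "Confirmed HIV-1 infection at any time prior to study entry". Treatment: "Participant should take ART for at least 2 years before baseline". Viral load: "Plasma viral load < 50 copies/ml for at least 2 years before baseline", with occasional blips allowed. No inclusion criterion calls for a detectable viral load before ART, and no exclusion criterion removes people who controlled HIV before ART.

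**Selection for interruption (Protocol 5.1.3).** Two laboratory thresholds apply: "Undetectable level of total HIV DNA" (below 66 copies per million PBMC) and undetectable unspliced cell-associated RNA (below 10 copies per million PBMC).

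**Background (Protocol 1.1).** On elite controllers: "The undetectable pVL in EC has been shown to be associated with low proviral DNA in peripheral blood CD4+ T cells". The same paragraph gives them little or no intracellular viral RNA. The four earlier in-house post-treatment controllers are described as virologically similar to elite controllers. They are also described as patients "who initiated cART during the chronic viremic phase, durably maintained control over viral replication" after stopping.

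**Objective and endpoint.** SAP 2.2: "The primary objective is to determine the proportion of post treatment controllers (PTC". Protocol 3.1 and SAP 2.3 and 4.1 count every participant with fewer than 50 copies/ml at week 48. Viral load before ART plays no part in the definition, and it is not a row in SAP Example Tables 6 or 8.

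**The concern.** The protocol treats spontaneous control and post-treatment control as different states and considers the second potentially more informative for cure strategies. The plan has no step that keeps them apart. A person whose viral load was already below 50 copies/ml before ART can meet every criterion in 4.2 and can pass the 5.1.3 thresholds. If that person simply returns to the pre-ART state after stopping, the endpoint records a success.

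Two results are exposed. One is the reading of the primary proportion, which rests on very few events. The other is the search for predictors of control, where one or two such people among a handful of controllers could make a marker of pre-ART control look like a marker of control after interruption. The planned Wilson interval reflects sampling error and does not cover this.

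**Working it through.** **1. Can a pre-ART controller pass each step?**

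| Step | Requirement | Excludes control before ART? |
|---|---|---|
| 4.2 infection | confirmed HIV-1 | no |
| 4.2 ART | at least 2 years | no; the reason for starting is not restricted |
| 4.2 viral load | <50 for at least 2 years before baseline | no; this period is on ART |
| 4.2 CD4 | current ≥500, nadir ≥300 (with an acute-infection exception) | no |
| 4.2 resistance | no history documented by genotyping | no; 5.1.1 collects assay results only if available |
| 4.2 subtype | listed subtypes | no; may imply an earlier sequence, but viraemic plasma is not required |
| 5.1.3 reservoir | DNA <66 and usRNA <10 per million PBMC | no; 1.1 gives both kinds of controller low values |
| Endpoint | <50 copies/ml at week 48 | no |

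**2. The plan's own figures (Protocol 4.3 and 8.4).** 643 × 7% = 45 patients pass the thresholds. 45 × 70% = 31.5, which the protocol takes as 32. Then 5% × 32 = 1.6 and 15% × 32 = 4.8, rounded to 2 and 5 controllers. The Wilson 95% interval is 1.7 to 20.1% for 2/32 (width 18.4 points) and 6.9 to 31.8% for 5/32 (width 24.9 points). This reproduces the stated 18 to 25 points.

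**3. Effect per person.** One person in the numerator is 1/32 = 3.1 points. With the denominator kept at 32 (assuming all 32 have a week-48 value), the result when such people are not counted as successes is:

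| Observed | One not counted | Two not counted |
|---|---|---|
| 2/32 = 6.3% (1.7 to 20.1) | 1/32 = 3.1% (0.6 to 15.7) | 0/32 = 0% (0 to 10.7) |
| 5/32 = 15.6% (6.9 to 31.8) | 4/32 = 12.5% (5.0 to 28.1) | 3/32 = 9.4% (3.2 to 24.2) |

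Viewed the other way, suppose one of the 32 is a pre-ART controller who stays suppressed. A true rate of 5% in the other 31 then appears as (1 + 0.05 × 31)/32 = 8.0%, and a true rate of 15% as (1 + 0.15 × 31)/32 = 17.7%.

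**4. Effect on Example Table 6.** One such person would be 1/2 = 50% of the controller column if there are 2 controllers, or 1/5 = 20% if there are 5.

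**5. How many such people?** The documents give neither the prevalence q of pre-ART controllers among those screened nor the share s that would pass both thresholds. As an assumption only, take q from 0.1% to 1% and s from 50% to 100%. The expected number among the interrupters is 643 × q × s × 0.70. This runs from 643 × 0.001 × 0.5 × 0.70 = 0.23 to 643 × 0.01 × 1 × 0.70 = 4.5. The range goes from well under one person to nearly all the expected controllers, so it gives no usable estimate.

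**The case against.** The strongest reply is that the trial defines a post-treatment controller operationally, as someone suppressed after stopping long-term ART, and uses that definition throughout both documents. Viraemia before ART is not part of it, so the planned proportion estimates what it sets out to estimate. This stands. A reader might infer that the primary estimate is biased upward as defined, or that the numerator must be redefined. The documents support neither. Redefinition would also do harm: a genuine controller whose old chart value is missing would drop out of the numerator, which at 5/32 moves 15.6% to 12.5%, the same 3.1 points.

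Further points stand in part:

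- Under Protocol 1.1 an elite controller has never been treated, so nobody with 2 years of ART is one. The issue concerns people who controlled HIV before they were treated.
- Section 1.2 mentions guidelines favouring earlier treatment. It does not say that spontaneous controllers are treated, and no such patient at these centres is described.
- Section 1.1 says low, while 5.1.3 requires undetectable. The share of spontaneous controllers who would pass is not given. The thresholds also fit true post-treatment controllers, so they are not wrong in themselves.
- Screening already takes medical and full antiretroviral history. The exploratory list in SAP 2.3 is open-ended, and its tables are only examples. Some row labels of Example Table 2 are missing from the available text, so a descriptive row for pre-ART viral load cannot be ruled out.

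None of this gives the analysis a way to show whether the week-48 controllers were viraemic before ART.

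**Conclusion.** The point holds as a gap in interpretation. Neither eligibility, nor the reservoir thresholds, nor the endpoint separates control that preceded ART from control that followed its interruption. The only firm size is 3.1 percentage points per person, assuming 32 interrupters in the denominator and that the person is below 50 copies/ml at week 48. The total effect is unknown and may be nil.

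A reader might infer from the small numbers that such people could account for the whole finding. That rests on prevalence and pass rates that the documents do not give, so it cannot be claimed. What can be said is that with 2 to 5 controllers expected, even one would matter to the interpretation, and the plan as written could not show it. This is a cheap improvement to the analysis and does not invalidate the design.

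**What to change.** Leave the primary endpoint and its denominator as defined, and make three additions:

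1. For every interrupter, record the last pre-ART plasma viral load(s), with dates, from the medical and antiretroviral history already taken at screening.
2. In SAP 4.1, before database lock, prespecify a sensitivity analysis that sorts week-48 controllers into three groups: pre-ART viraemia documented, pre-ART viral load below 50 copies/ml documented, and pre-ART value not available. State how several values for one person are combined. Give the proportion with its Wilson 95% interval for all interrupters, then again with the same denominator but without counting as successes those documented below 50. Show the second figure both ways for missing values. For example, with 5 controllers of whom one is documented below 50 and one has no value, report 5/32 (15.6%), 4/32 (12.5%, missing counted as success) and 3/32 (9.4%, missing not counted).
3. Add pre-ART viral load as a candidate predictor in SAP 2.3 and in Example Tables 6 and 8.

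The cost is one retrospective chart variable for about 32 people and a few lines in the SAP. Some old values will be missing, which is why they form their own group. No participant is dropped and no study procedure changes.

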# **S**YNOPSIS

31NUP313	
ΗΥΡΟΤΗΕSIS	Analytical interruption of longstanding antiretroviral therapy (ART) in HIV-1 infected patients with a very low proviral reservoir results in "functional cure".
DESIGN	Prospective observational study.
STUDY SITE & POPULATION	HIV-1 infected patients with normal peripheral blood CD4 T-cell counts and undetectable viral load will be recruited in four Belgian HIV reference centers: Institute of Tropical Medicine Antwerp, University Hospital Ghent, University Hospital Brussel, Saint-Pierre University Hospital.
DURATION	9 months screening + 48 weeks clinical study + 12 weeks post study. (23 months in total until last patient visit)
OBJECTIVES AND ENDPOINTS	The primary objective is to evaluate the proportion of patients with low proviral reservoir that have a sustained viral suppression after 48 weeks of treatment interruption.
INCLUSION & EXCLUSION CRITERIA	HIV-1 infected adults with peripheral blood CD4 T-cell counts >= 500/μL and plasma viral load < 50 copies/ ml will be evaluated for inclusion. HBV or HCV co-infected patients and patients with ongoing HIV-related diseases or a history of antiretroviral drug resistance or AIDS event will be excluded.
SCREENING, RECRUITMENT & RANDOMIZATION	Two-step screening: viral reservoir measurement and analytical treatment interruption. There is no randomization foreseen
INTERVENTION	Interruption of antiretroviral treatment in HIV-1 infected patients with low viral reservoir.
FOLLOW-UP	Intensive clinical and laboratory follow-up during 48 weeks followed by 12 weeks post intervention.
ANALYTICAL METHODS	Total HIV PCR for plasma viral RNA, for cell- associated viral RNA and DNA will be quantified using droplet (digital PCR droplet). Viral outgrowth assay (limiting dilution culture of CD4 T cells).
SAFETY	Safety of the intervention will be evaluated by recording (Serious) Adverse Events and grading laboratory parameters and vital signs. Data will be monitored by means of a sponsor regulated pharmacovigilance system.

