# 4.3 Study feasibility and sample size

In 2012, the number of HIV-infected patients in medical follow-up was estimated at 13,352 for Belgium and 5,241 for Flanders.

A thorough review of the research databases and clinical files of the four participating centers was conducted in order to estimate the sample size of the study population and the feasibility of the study.

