### **Step 3: Inclusion and exclusion criteria**

According to the above described inclusion and exclusion criteria, a total of 643 potential participants can be selected for trial participation and measurement of viral reservoir during the screening period of 9 months (ITG 228, UZG 125, VUB 64, UMC St Pieter 226). This corresponds to approximately 10% of the total number of patients currently being under anti-retroviral treatment.

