# 4.5 Withdrawal and termination of the study

In accordance with the Declaration of Helsinki, ICH Good Clinical Practice Guidelines and the Belgian Law of 2004, a participant has the right to withdraw from the study at any time for any reason without prejudice to his/her future medical care by the physician at the institution. The Investigator also has the right to withdraw patients from the study if one or more of the following events occur:

- Consent withdrawal,
- Significant protocol violation or noncompliance on the part of the participant
- Refusal of the participant to continue observations
- Unacceptable adverse events (AEs)
- Unrelated serious medical illness or complication
- Criteria for cART re-initiation met based on viral rebound (see section 5.1.5 below),
- Pregnancy
- Decision by the Investigator that termination is in the patient's best medical interest. This includes, but is not limited to, new clinical events, even if not related to the study procedure, ongoing risk of HIV transmission (e.g. new sexually transmitted infections) and unprotected sexual contact with seronegative partner(s).
- Lost to follow-up, as defined further in this section.

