# **5.1.1 FIRST ELIGIBILITY SCREENING AND INCLUSION IN THE FIRST PART OF THE STUDY** (RESERVOIR MEASUREMENT STUDY)

Study participants will be selected from the four participating clinical centers. Screening evaluations to determine eligibility must be completed within 7 days prior to study entry.

The patient will be invited to participate in the trial and provided information about the aims and risks of the project. After obtaining written informed consent (first written informed consent), clinical eligibility will be assessed. Patients will be eligible for enrollment if they fulfill all of the inclusion criteria described in section 4.2. Patients will not be eligible for the study if they meet any of the above described exclusion criteria.

3x9ml blood will be drawn in order to evaluate the magnitude of the viral reservoir. This sample will be sent to UZ Gent for quantification of total HIV DNA and unspliced cell-associated RNA. More information on the method used is to be found in section 5.3 of the protocol.

The following will be assessed at this visit:

- Assessment of subject eligibility according to the inclusion and exclusion criteria
- Demographic and epidemiological data
- Medical history (past and current), including HIV-associated conditions
- Full antiretroviral history (including result of resistance assays if available)
- Review of non-antiretroviral medication within the last 30 days
- Physical examination including vital parameters, height and weight
- HIV viral load and CD4 T cell count.

- Laboratory test (non-fasting): hemoglobin, absolute neutrophil count (ANC), platelets, creatinine, liver enzymes AST & ALT. Hepatitis HCV & HBV serology if necessary.

- Pregnancy test among women.

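### The operative hepatitis exclusion is narrower than the synopsis and rests on an undefined, unscheduled measure of replication, so it can admit an HBsAg-positive patient to a treatment interruption

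*Protocol*

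**What the plan says.** The synopsis row on inclusion and exclusion criteria lists "HBV or HCV co-infected patients and patients with ongoing HIV-related diseases" among those who will be excluded. It does not restrict this to active infection.

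Protocol 4.2 restricts the exclusion to active hepatitis B or C, "as defined with a positive serology for either disease with signs of active viral replication". In the text as read, a question mark follows. Section 5.1.1 applies the 4.2 list rather than the synopsis: "Patients will not be eligible for the study if they meet any of the above described exclusion criteria".

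On testing, Table 1 marks HBs antibody, HBc antibody, HBs antigen and HCV antibody at Screening 1, whereas the text of 5.1.1 asks for "Hepatitis HCV & HBV serology if necessary". HBV DNA and HCV RNA appear nowhere in Tables 1, 2 or 3 or in the baseline list in 5.1.5. The SAP does not define the criterion.

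Protocol 4.3 counts candidates under the 4.2 criteria: "According to the above described inclusion and exclusion criteria, a total of 643 potential participants can be selected".

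**The concern.** The only intervention in this trial is stopping antiretrovirals, so a hepatitis exclusion is a safety criterion. Its operative wording protects less than the synopsis suggests and cannot be applied uniformly. One site may take HBs antigen as a sign of replication, while another may ask for a viral load that the protocol does not schedule.

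For HBV there is a further problem of timing. Replication is judged while the patient is still on treatment. If the regimen contains a drug that also suppresses HBV, an HBsAg-positive patient may show no sign of replication at screening and so pass 4.2. That some antiretrovirals act on HBV is not stated in the documents and is for the sponsor's clinicians to confirm. The documents do show that nucleoside analogues will be among the drugs stopped: 5.1.5 plans a nucleoside tail for some regimens, and the three regimen classes named in SAP Example Table 2 all include an NRTI. That table also has a row for other regimens, and 4.2 allows mono- and bitherapy. The documents do not give the share of participants on an HBV-active drug.

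For HCV the problem is only whether the criterion can be decided, because antibody is the one scheduled test.

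**Working it through.** **The rules side by side, for an HBsAg-positive patient with no evident replication on treatment**

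| Place | Rule | Outcome |
|---|---|---|
| Synopsis | Co-infected patients excluded | Excluded |
| 4.2, hepatitis criterion | Positive serology plus signs of replication | Not excluded if no sign is found |
| 4.2, liver enzymes | Confirmed AST and/or ALT above 5 x ULN | Excluded only if enzymes are that high on treatment |
| 4.2, general condition | Investigator's judgement on adherence or safety | May be excluded |

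**What is scheduled.** Serology is at Screening 1 only. AST/ALT is measured at Screening 1, at baseline, at weeks 4, 12, 20, 32 and 48, and at the End of Study visit, then only if indicated (Tables 1 to 3). From baseline, the gaps between scheduled enzyme checks are 4, 8, 8, 12 and 16 weeks for a participant who stays suppressed. A participant who rebounds is also checked at End of Study. No hepatitis test follows screening, and the restart criteria in 5.1.7 do not name liver enzymes.

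**Cost of the HBsAg rule in candidates.** Inputs from Protocol 4.3: 643 candidates, 7% qualifying and 30% declining.

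- The plan's figure: 643 x 0.07 = 45.0, and 45.0 x 0.70 = 31.5, which the protocol gives as 32.
- The HBsAg-positive share q is not in the documents. Assume 1% to 5%.
- q = 1%: 643 x 0.01 = 6.4 candidates lost; 643 x 0.99 x 0.07 x 0.70 = 31.2.
- q = 5%: 643 x 0.05 = 32.2 candidates lost; 643 x 0.95 x 0.07 x 0.70 = 29.9.

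**Cost in precision.** Wilson 95% width = [2z / (1 + z²/n)] x √[p(1 − p)/n + z²/(4n²)], with z = 1.96. For 2 of 32 this is 3.500 x √(0.001831 + 0.000938) = 0.184.

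| Case | n = 32 | n = 30 | Increase (points) |
|---|---|---|---|
| 2 controllers | 18.4 | 19.5 | 1.1 |
| 5 controllers | 24.9 | 26.2 | 1.3 |
| Rate fixed at 5% | 17.2 | 17.9 | 0.7 |
| Rate fixed at 15% | 24.6 | 25.3 | 0.8 |

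The first two rows at n = 32 reproduce the 18 to 25 points in Protocol 8.4. Holding the counts at 2 and 5 while n falls raises the implied rate, so the fixed-rate rows are the fairer measure of cost: under 1 point, at the upper end of the assumed range.

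**The case against.** The strongest reply is that the plan has more protection than the hepatitis line alone suggests. Section 4.2 also excludes any condition "that might interfere with adherence to study requirements or safety of the participant". Criteria are re-checked at Screening 2 and baseline, with AST/ALT at baseline. Each of the 12 visits after interruption includes a physical examination and adverse event assessment, and 7.1 records clinically significant laboratory abnormalities as adverse events. Unscheduled visits are allowed. Section 5.1.7 requires restart once a new significant clinical condition is documented, which a hepatitis flare could plausibly meet, and 4.5 lets the investigator withdraw a patient. This stands: the 4- to 16-week gaps are gaps in scheduled enzymes, not in clinical surveillance, and it would be wrong to infer that participants are unprotected. But none of these provisions is specific to hepatitis. The re-checks apply the same undefined criterion, most of the rest depends on judgement, and surveillance, withdrawal and restart act only after treatment has stopped.

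A second reply is that replication status may already be on file. Candidates come from regular follow-up at the reference centers, medical history is taken, and for the candidate count "A thorough review of the research databases and clinical files of the four participating centers was conducted". A reader might infer from the missing tests that nobody will know the status; the documents do not show that. They also do not require a result on file or say which result decides.

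A third reply is that a synopsis abbreviates, and that co-infected may be shorthand for active infection. That is possible. It leaves two readings of a safety rule, and sites apply the narrower text.

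**Conclusion.** The point holds as an inconsistency between the synopsis and 4.2, plus an operative criterion that is undefined and that no scheduled test measures. If the question mark is an artefact of text reading, the rest is unchanged. For HBV it goes beyond missing detail, because 4.2 taken literally can admit a patient whom the synopsis excludes. The seriousness of that rests on the clinical premise about HBV-active antiretrovirals, which lies outside the documents.

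Stronger readings are tempting and unsupported. The documents do not show that any such patient would be enrolled: they give no HBV or HCV prevalence, so the number affected is unknown. They do not support an equal safety argument for HCV, where the defect is decidability only. No sample size, interval width or analysis in the protocol or SAP is wrong because of this.

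**What to change.** Delete the question mark. State in both the synopsis and 4.2 that HBsAg-positive patients are excluded, decided on the HBs antigen test already in Table 1. In 5.1.1, replace the conditional wording on hepatitis serology with a requirement to test at Screening 1 unless a recent documented result exists, and define recent.

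For HCV, make the synopsis and 4.2 say the same thing and let the sponsor's clinicians choose the deciding test. An antibody-only exclusion could remove people who have cleared the infection, so it is not proposed here. Isolated HBc antibody is also for the clinicians to settle.

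This changes wording in three places and adds no new type of test to the schedule. The price is a few candidates: 6 to 32 of 643 under the assumed 1% to 5%, or roughly 0.3 to 1.6 expected interrupters (31.5 − 31.2 and 31.5 − 29.9). That is small against having a safety exclusion that every site can apply in the same way.
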